## 11.6 Multiple Imputation Method

The MI procedure will be performed for the primary analysis using the following methods:

Missing data for 3 months after last treatment Blinded Evaluator GCRS assessment will be imputed using MI under the Missing at Random (MAR) assumption. Change from Baseline in Blinded Evaluator 3 months after last treatment GCRS will be derived from the corresponding imputed values. The following steps will be followed to create the imputations:

1. Regardless of the actual pattern of missing data, the Markov Chain Monte Carlo (MCMC) method of the SAS PROC MI procedure will first be used to make it monotone. The single chain method will be used. The minimum values for imputed variables will be set to 0, in order to force PROC MI to redraw another value for imputation when an intended imputed value is less than the 0, the maximum value for imputed variables will be set to 3, in order to force PROC MI to redraw another value for imputation when an intended imputed value is greater than the 3. Imputed values will be rounded to the nearest integer. The seed number will be set to 2208 and 5 imputations will be created.
2. The SAS PROC MI will be used for imputing missing values of data with monotone missing pattern. One imputation will be made using each of the 5 MCMC-imputed datasets (Step 1). A linear regression model will be used with covariates for treatment, site, race group, ethnicity, sex, Fitzpatrick Skin Type, age, total injection volume, and non-missing GCRS values from earlier scheduled time points including Baseline. The minimum values for imputed variables will be set to 0, in order to force PROC MI to redraw another value for imputation when an intended imputed value is less than the 0. Imputed values will be rounded to the nearest integer. The seed number will be set to

Galderma

Protocol number: 43USCH2208

Protocol V4.0

2208. Change from Baseline in 3 months after baseline GCRS will be derived from the corresponding imputed values. The Lost to Follow Up subjects who were reenrolled described in [Section 9.1.1](#) and [9.1.2](#) will be handled assuming No Change from Baseline after the missing values have been imputed with multiple imputation. Protocol deviations will be used to identify subjects who missed their primary endpoint visit due to being Lost to Follow Up and later reenrolled.

3. The imputed datasets will be analyzed as specified in [Section 9.1.2](#).
4. The results from the mixed model analysis on the imputed datasets will then be combined using the SAS PROC MIANALYZE to produce a single set of statistics.

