9.6 Handling of missing data

Number of missing values will be summarized and reported as appropriate.

For ITT analysis of the responder rate based on the Blinded Evaluators' live assessment of the GCRS, at 3 months after last treatment, the analysis will be performed using multiple imputation (MI) as the primary imputation method.

Impact of missing data on the primary endpoint will be evaluated by performing sensitivity analysis based on the baseline observation carried forward (BOCF) method, and the observed cases in the ITT set.

All other effectiveness endpoints will be evaluated based on the observed cases in ITT.

Descriptive statistics of all safety data will be performed on observed cases in the Safety population.

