## 9.2 Secondary Effectiveness Analysis

Secondary effectiveness analysis will be evaluated based on the OC in ITT Population, unless otherwise indicated.

P-values obtained for any endpoint other than the primary will only be provided for ease of interpretation of results. All other secondary effectiveness analyses will be performed descriptively only.

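### The primary multiple imputation uses floored, rounded normal draws and only 5 imputations, which adds avoidable bias and seed noise that matter if the ITT limit falls near a threshold

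*SAP*

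**What the plan says.** - SAP 9.1.2 bases the primary ITT analysis on multiply imputed Month 3 Blinded Evaluator GCRS. The upper 95% limit for test minus comparator is compared with 0.5 for non-inferiority and with 0 for superiority. Non-inferiority must hold in both ITT and PP; superiority is then read from ITT only. SAP 9.1.3 analyses PP on observed cases.
- SAP 11.6, Step 1 (MCMC, to reach a monotone pattern) sets a floor of 0 by redrawing, and "the maximum value for imputed variables will be set to 3". It continues: "Imputed values will be rounded to the nearest integer. The seed number will be set to 2208 and 5 imputations will be created".
- SAP 11.6, Step 2 (linear regression, one draw per Step 1 dataset) keeps the floor, "in order to force PROC MI to redraw another value for imputation when an intended imputed value is less than the 0", and the rounding, but states no maximum. PROC MIANALYZE then combines the results.
- The SAP gives no reason for 5 imputations and plans no check of Monte Carlo error.
- Protocol 9.6 assigns multiple imputation as follows: "For ITT analysis of the responder rate based on the Blinded Evaluators". SAP 11.1 assigns it to the change from baseline instead, and SAP 9.2 states "Secondary effectiveness analysis will be evaluated based on the OC in ITT Population, unless otherwise indicated". SAP 15.2 lists two changes from the protocol, and this is not one of them.

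**The concern.** The GCRS runs from 0 to 3, and the ordinal model in SAP 9.1.3 takes baseline grades 1 and 2, so a subject who improves by one grade ends at 0 or 1. A normal draw around such a value often falls below 0. Discarding those draws and keeping the rest raises the mean of what is imputed, and the rise is largest where the predicted score is lowest.

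Change is Month 3 minus baseline, so a positive difference means that the test product did worse. If it truly did worse by about 0.5, the comparator arm sits nearer the floor. Its imputed scores are then pushed up more and the difference shrinks towards a pass, which is the anti-conservative direction for non-inferiority.

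Separately, with only 5 imputations the pooled limit depends visibly on the seed. A seed fixed in advance prevents choosing among results, but it does not remove that noise.

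**Working it through.** **Inputs.** From SAP 3.2.3: margin 0.5, true difference 0.1, SD 0.7, 2:1 allocation (116:58), 90% power, two-sided 95% CI, and about 15% dropouts and non-evaluable subjects. From SAP 11.6: 5 imputations, floor 0, rounding. Assumed: Month 3 scores near 0, baseline grades 1 and 2 in equal numbers, data missing completely at random within arm, and 5% to 15% missing. The simulations cover Step 2; Step 1 acts only on non-monotone patterns.

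**1. The plan's own figure.** Comparator n = (1.96 + 1.2816)² × 0.7² × (1 + 1/2) / (0.5 − 0.1)² = 48.3, so 49 and 147 in total. 147 / 0.85 = 172.9, so 173, and 174 as the next multiple of 3. The plan's 147 and 174 reproduce.

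**2. One draw.** Take a predicted mean of 0.3 and SD 0.6.
- Bound first, then round. P(draw ≥ 0) = Φ(0.5) = 0.691. P(0) = (Φ(0.333) − Φ(−0.5)) / 0.691 = 0.466; P(1) = 0.501; P(2) = 0.033. The mean is about 0.57.
- Round first, then bound. Draws below −0.5 are discarded; P(draw ≥ −0.5) = 0.909. P(0) = 0.593; P(1) = 0.381; P(2) = 0.025. The mean is about 0.43.

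The SAP does not state the order. Both results exceed 0.3.

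**3. Bias of imputed scores.** Step 2 was simulated at N = 174 and compared with unbounded, unrounded draws. The bias was +0.07 to +0.18 grade for mean changes of about −0.45 to −0.8, and +0.04 to +0.10 for a mean change near −0.1. It was upward in every setting.

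**4. Effect on the treatment difference.** At about the planned difference with equal missingness, the shift was at most 0.004 in absolute value. Further simulated cases, shown as missing in test / comparator:

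| Missing | True difference | Planned imputation | Shift |
|---|---|---|---|
| equal | 0.081 | 0.077 | −0.004 |
| 15% / 15% | 0.473 | 0.451 | −0.022 |
| 15% / 15% | 0.519 | 0.496 | −0.023 |
| 5% / 20% | 0.518 | 0.476 | −0.042 |
| 20% / 5% | 0.474 | 0.486 | +0.012 |
| 20% / 5% | 0.230 | 0.252 | +0.022 |
| 20% / 5% | 0 | +0.024 | +0.024 |
| 5% / 20% | 0 | −0.023 | −0.023 |

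Rounding before the bound check roughly halves such shifts: in comparable 20% / 5% settings, +0.026 fell to +0.012. That gives about 0.01 to 0.02 for the 15% / 15% rows near the margin.

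**5. Seed noise.** SE at 174 = 0.7 × √(1/116 + 1/58) = 0.1126. With 15% missing information, B ≈ 0.15 × 0.1126² / 0.85 = 0.00224. The Monte Carlo SD of the pooled estimate is √(B/m): 0.021 for m = 5 and 0.0047 for m = 100. Simulated SD of the upper limit across seeds:

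| Missing | m = 5 | Central 95% range, m = 5 | m = 100 |
|---|---|---|---|
| 5% | 0.011-0.016 | 0.04-0.06 wide | 0.002-0.003 |
| 10% | 0.016-0.023 | 0.06-0.08 wide | 0.004-0.005 |
| 15% | 0.023-0.030 | 0.08-0.11 wide | 0.005-0.006 |

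This noise comes from m = 5. Unbounded draws vary as much or slightly more.

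**6. Distance to the margin.** Expected upper limit at the design point = 0.1 + 1.96 × 0.1126 = 0.32, which is 0.18 below 0.5. That is 0.18 / 0.030 = 6 of the largest seed SDs.

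**7. Missing maximum in Step 2.** For predicted means up to 1.2 with SD 0.6, the chance of rounding above 3 is 1 − Φ((3.5 − 1.2)/0.6), which is below 0.01%.

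**The case against.** The strongest reply is that little of this reaches the decision.

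- **Two analyses must pass.** PP on observed cases has no imputation and no seed. In 2,500 simulated trials per setting at a true difference of 0.5, with observed cases in all subjects standing in for PP, false non-inferiority at 15% / 15% missing was 3.5% on ITT alone but 2.2% when both had to pass. At 5% missing the figures were 2.1% and 1.6%. The simulation error is about √(0.025 × 0.975 / 2500) = 0.3 percentage points. This stands for non-inferiority; it does not help superiority.
- **Power is barely touched.** Near the planned 0.1 difference with 15% / 15% missing, simulated ITT power was 97.2% as planned and 96.8% on observed cases. This stands.
- **Five imputations are not invalid.** Rubin's rules widen the interval for small m. With 5 unbounded imputations, error at the margin was 2.6% at 15% missing. A reader might infer that the primary interval is invalid because m = 5. That does not follow; the cost is reproducibility.
- **15% is an upper guide.** It includes protocol-deviation exclusions, while SAP 9.1.1 keeps observed values after prohibited treatment, hyaluronidase and mis-administered treatment. This stands, so the 5% row belongs beside the 15% row.
- **Sensitivity analyses exist.** SAP 9.1.3 plans observed-case, BOCF, worst-case and ordinal analyses. They would reveal a discrepancy, but they do not replace the primary limit.
- **Responder rate.** A reader might infer from Protocol 9.6 that responders must be imputed. The same section goes on to test missing-data impact on the primary endpoint and puts all other effectiveness endpoints on observed cases. SAP 11.1 makes the same provision for change from baseline. A drafting slip is the likelier reading.

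**Conclusion.** The point holds with limited reach. Under the assumptions listed, the planned draw inflates imputed GCRS by roughly 0.04 to 0.18 grade. That largely cancels at the planned difference with equal missingness, but it favours a pass near the 0.5 margin, and it shifts the difference in either direction when missingness differs by arm. Five imputations add an avoidable seed SD of about 0.01 to 0.03 to the ITT upper limit.

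A reader might infer that the seed could decide the trial. The documents do not support that: under the design assumptions the limit is far from 0.5, the seed is fixed in advance, and PP must also pass. What remains is a result close to 0.5, or close to 0 for superiority, where the ITT limit alone decides. Step 2's missing maximum is an inconsistency with negligible effect.

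The text of SAP 11.6 is certain. The sizes depend on an assumed Month 3 distribution, on the order of bounding and rounding, and on the share and pattern of missing data.

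**What to change.** In SAP 11.6:

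1. Use at least 100 imputations. The pre-specified seed can stay.
2. Impute the Month 3 score with an ordinal (cumulative-logit) model or by predictive mean matching restricted to 0-3. Floor, maximum, redraws and rounding then fall away.

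In SAP 15.2, list that multiple imputation is applied to the change from baseline rather than to the responder rate named in Protocol 9.6. A responder imputation is not required.

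The cost is SAP wording, minutes of computing, and possibly merging sparse site levels so that the ordinal model converges. Data collection and sample size do not change.

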## 12 Interim Analysis and Data Monitoring

No interim analysis is planned for this study.

## 13 Quality Control

All data displays and analyses will adhere to the International Conference on Harmonization (ICH) *Harmonized Tripartite Guideline: Structure and Content of Clinical Study Reports (ICH Topic E3)*.

All analyses will be performed using SAS® Version 9.4 (or later). CCI will follow its standard operating procedures in the creation and quality control of all tables, listings, figures, and analyses. The Sponsor or its designee will review all tables, listings, and figures prior to final database lock. All final SAS programs and associated output files will be transferred to the Sponsor in agreed-upon format at project completion.

## 14 Tables and Listings Conventions

Mock-ups for statistical tables and listings will be provided. Final formats for the statistical tables and listings may deviate from these mock-ups upon agreement with the Sponsor. Footnotes will be used as needed to clarify the information that is presented in the tables and listings. Unless otherwise requested by the Sponsor, the term ‘subject’ will be used in all tables and listings, in accordance with Clinical Data Interchange Standards Consortium (CDISC) standards.

The table and listing mock shells, along with their programming convention, will be provided in a separate document.

Effective date: 2024-05-29 18:37

Galderma

Protocol number: 43USCH2208

Protocol V4.0

[figure not shown]
## 15 Changes to Planned Analyses

### 15.1 Changes to Planned Analyses

This is the first version of the SAP for the study.

### 15.2 Changes in Analysis Planned in Protocol

The Investigator Satisfaction Questionnaire is collected at the subject level instead of the investigator level. Due to the nature of the questionnaire, the analysis in the SAP differs from the protocol definition for this endpoint. [Sections 3.2.4.8](#) and [9.2.8](#) have been updated to reflect these changes.

The protocol reads that “If the PP Population contains less than 90% of the subjects in the ITT, a sensitivity analysis of the primary effectiveness endpoint will be performed based on the PP Population. Regardless of the amount of overlap between the PP Population and the ITT Population, a sensitivity analysis will be performed using the PP Population. [Sections 5.2](#) and [9.1.3](#) have been updated to reflect these changes.

Effective

Version: 1.0

|   |  |                                   |
|---|--|-----------------------------------|
| 
GALDERMA
<small>EST. 1981</small>
 | 
Title
43USCH2208 Statistical Analysis Plan (SAP)
 | 
Doc id
MA-60980
 |
|---|--|-----------------------------------|

Effective date: 2024-05-29 18:37

[figure not shown]
Galderma

Protocol number: 43USCH2208

Protocol V4.0

## 16 Appendices

### 16.1 Study Flow Chart

Effective

Version: 1.0

Confidential

Statistical Analysis Plan Version #1.0

Page 50 of 63

|   |  |                                       |
|---|--|---------------------------------------|
| 
GALDERMA
 
631,1581
 | 
Title
 
43USCH2208 Statistical Analysis Plan (SAP)
 | 
Doc id
 
MA-60980
 |
|---|--|---------------------------------------|

Effective date: 2024-05-29 18:37

Galderma

Protocol number: 43USCH2208

Protocol V4.0

Effective

Version: 1.0

|   |  |   |
|---|--|---|
| 

GALDERMA

631,1581

 | 

Title

43USCH2208 Statistical Analysis Plan (SAP)

 | 

Doc id

MA-60980

 |
|---|--|---|

Effective date: 2024-05-29 18:37

Galderma

Protocol number: 43USCH2208

Protocol V4.0

Effective

Version: 1.0

GALDERMA

(S/N: 1581)

Title

43USCH2208 Statistical Analysis Plan (SAP)

Doc id

MA-60980

Galderma

Protocol number: 43USCH2208

Protocol V4.0

*Effective*

Effective date: 2024-05-29 18:37

Version: 1.0

GALDERMA

Title  
43USCH2208 Statistical Analysis Plan (SAP)

Doc id  
MA-60980

Galderma

Protocol number: 43USCH2208

Protocol V4.0

*Effective*

Effective date: 2024-05-29 18:37

Version: 1.0

Confidential

Statistical Analysis Plan Version #1.0

Page 54 of 63

GALDERMA

Title  
43USCH2208 Statistical Analysis Plan (SAP)

Doc id  
MA-60980

Effective date: 2024-05-29 18:37

Galderma

Protocol number: 43USCH2208

Protocol V4.0

Effective

Version: 1.0

GALDERMA

(S/N: 1181)

Title  
43USCH2208 Statistical Analysis Plan (SAP)

Doc id  
MA-60980

Effective date: 2024-05-29 18:37

Galderma

Protocol number: 43USCH2208

Protocol V4.0

Effective

Version: 1.0

Confidential

Statistical Analysis Plan Version #1.0

Page 56 of 63

GALDERMA

(S/N: 1581)

Title  
43USCH2208 Statistical Analysis Plan (SAP)

Doc id

MA-60980

Effective date: 2024-05-29 18:37

Galderma

Protocol number: 43USCH2208

Protocol V4.0

*Effective*

Version: 1.0

Confidential

Statistical Analysis Plan Version #1.0

Page 57 of 63

GALDERMA

Title  
43USCH2208 Statistical Analysis Plan (SAP)

Doc id  
MA-60980

Effective date: 2024-05-29 18:37

Galderma

Protocol number: 43USCH2208

Protocol V4.0

Effective

Version: 1.0

Confidential

Statistical Analysis Plan Version #1.0

Page 58 of 63

|   |  |   |
|---|--|---|
| 

GALDERMA

631,1581

 | 

Title

43USCH2208 Statistical Analysis Plan (SAP)

 | 

Doc id

MA-60980

 |
|---|--|---|

Effective date: 2024-05-29 18:37

Galderma

Protocol number: 43USCH2208

Protocol V4.0

Effective

Version: 1.0

Confidential

Statistical Analysis Plan Version #1.0

Page 59 of 63

GALDERMA

Title  
43USCH2208 Statistical Analysis Plan (SAP)

[figure not shown]
Doc id  
MA-60980

Effective date: 2024-05-29 18:37

Galderma

Protocol number: 43USCH2208

Protocol V4.0

Effective

Version: 1.0

GALDERMA

Title  
43USCH2208 Statistical Analysis Plan (SAP)

Doc id  
MA-60980

Galderma

Protocol number: 43USCH2208

Protocol V4.0

Effective

Effective date: 2024-05-29 18:37

Version: 1.0

Confidential

Statistical Analysis Plan Version #1.0

Page 61 of 63

GALDERMA

Title  
43USCH2208 Statistical Analysis Plan (SAP)

Doc id  
MA-60980

Effective date: 2024-05-29 18:37

Galderma

Protocol number: 43USCH2208

Protocol V4.0

Effective

Version: 1.0

Confidential

Statistical Analysis Plan Version #1.0

Page 62 of 63

GALDERMA

Title  
43USCH2208 Statistical Analysis Plan (SAP)

Doc id  
MA-60980

Effective date: 2024-05-29 18:37

Galderma

Protocol number: 43USCH2208

Protocol V4.0

Effective

Version: 1.0

Confidential

Statistical Analysis Plan Version #1.0

Page 63 of 63

GALDERMA

03/1/2021

Title  
43USCH2208 Statistical Analysis Plan (SAP)

Doc id

MA-60980

Effective date: 2024-05-29 18:37

